#### 9.3. Clinical Laboratory Tests

#### 9.3.1. Laboratory Value Definitions

Laboratory values and change from baseline values will be summarized descriptively by visit. Baseline will be determined according to Section 4.1.3. If there are multiple values that meet the criteria for baseline, the value from the central laboratory has priority over the value from the local laboratory. Thereafter, additional rules may be provided after consultation with the medical monitor to delineate which value will be defined as baseline.

Laboratory test values will be assessed for severity based on the numerical component of CTCAE v4.03.

#### 9.3.2. Laboratory Value Summaries

All test results and associated normal ranges from central laboratories will be reported in SI units. Any laboratory test results and associated normal ranges from local laboratories will be converted to SI units.

When there are multiple laboratory nonmissing values for a participant's particular test at a scheduled visit, central laboratory values have higher priority over local laboratory values. If a tie still exists, the laboratory value with the smallest laboratory sequence number will be used in by-visit summaries.

Numeric laboratory values will be summarized descriptively in SI units, and non-numeric test values will be tabulated when necessary. In addition, line graphs will be provided for ALT, AST, hemoglobin, platelet counts, leukocytes, neutrophils, and lymphocytes.

Shift tables will be presented showing change in CTCAE grade from baseline to worst grade postbaseline. Separate summaries for abnormally high and abnormally low laboratory values will be provided when the laboratory parameter has both high and low grading criteria. The denominator for the percentage calculation will be the number of participants in the baseline category. The number of participants who experienced worsening of laboratory abnormalities will be summarized by maximum postbaseline severity.

#### 9.3.3. Potential Hy's Law Events

Participants with elevated ALT or AST >  $3 \times \text{ULN}$  range and alkaline phosphatase <  $2 \times \text{ULN}$  range accompanied by total bilirubin >  $2 \times \text{ULN}$  range at the same visit will be listed by treatment group.

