5.4.1.1. Dose Modifications

Dose modification guidance for AEs that have been previously observed in subjects receiving INCB050465 or are potential class-effect AEs are provided (see Table 3 and Table 5). The starting dose and dose reduction levels of INCB050465 are provided (see Table 4). Individual decisions regarding dose interruption and reduction should be made using clinical judgment and in consultation with the sponsor's medical monitor, taking into account relatedness of the AE to the study treatment and the subject's underlying condition. Adverse events that have a clear alternative explanation or transient (≤ 72 hours) abnormal laboratory values without associated clinically significant signs or symptoms may be exempt from dose-reduction guidelines.

Table 3: Guidelines for Interruption and Restarting INCB050465

ADVERSE EVENT	ACTION TAKEN
Chemistry	

 AST and/or ALT is Grade 3 ($> 5.0 \times \text{ULN}$). Note: In subjects with liver metastasis-related elevations at baseline, contact sponsor to discuss clinical management and possible dose reductions.	
Step 1: Interrupt INCB050465 and monitor weekly until the toxicity has resolved to \leq Grade 1.
 
Step 2: Restart INCB050465 at next lower dose with medical monitor approval. Monitor as clinically indicated.

Hematology	

 Grade 3 ANC ($< 1.0 \times 10^9/\text{L}$). Platelet count is Grade 2 (50 to $< 75 \times 10^9/\text{L}$) for subjects who enrolled with platelets $> 100 \times 10^9/\text{L}$. Platelet count is Grade 3 ($< 50 \times 10^9/\text{L}$) for subjects who enrolled with platelets $\leq 100 \times 10^9/\text{L}$. 	
Step 1: Interrupt INCB050465 up to 14 days until the toxicity has resolved to \leq Grade 1 or pretherapy baseline. For Grade 3 ANC, monitor at least weekly.
 
Step 2: Restart INCB050465 at same dose; monitor as clinically indicated.

 Grade 4 ANC ($< 0.5 \times 10^9/\text{L}$). Grade 3 or Grade 4 febrile neutropenia. Platelet count is Grade 4 ($< 25 \times 10^9/\text{L}$). 	
Step 1: Interrupt INCB050465 up to 14 days until the toxicity has resolved \leq Grade 2. (Monitor ANC at least weekly.)
 
Step 2: Restart INCB050465 at same dose. Monitor as clinically indicated. If recurs, start at next lower dose.

Table 3: Guidelines for Interruption and Restarting INCB050465 (Continued)

ADVERSE EVENT	ACTION TAKEN
Other toxicities	

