- ^f Required at baseline except for reasons provided in Section 7.6.2. If disease is present in bone marrow at baseline, a bone marrow biopsy is required to confirm CR.
- ^g PJP prophylaxis will continue for 2 to 6 months after the last dose of study treatment.
- ^h [REDACTED]
- ⁱ May be conducted by phone or email.

Table 7: Schedule of Laboratory Assessments

Laboratory Tests	Section	Screening	Treatment				EOT	Safety Follow-Up
		Day -28 to -1	Day 1	Every 4 Weeks Through Week 48 (± 3 Days)	Every 12 Weeks From Week 48 (± 1 Week)	Other		EOT + 30-35 Days
Serum chemistries	7.5.6.1	X	X ^a	X	X		X	X
Hematology ^b	7.5.6.1	X	X ^a	X	X	X ^c	X	X
Serology	7.5.6.3	X				X ^d	X	
Serum pregnancy	7.5.6.2	X ^e					X	X
Urine pregnancy	7.5.6.2					X ^f		
HIV testing	7.5.6.4	X ^g						
Tumor biopsy	7.8.5	X ¹				X ¹		

^a Day 1 assessments may be omitted if the screening tests occurred in the preceding 7 days. If needed, Day 1 blood draws should be performed before administration of study treatment.

^b Hematology samples will be collected every 2 weeks for the first 8 weeks.

^c Week 2 and Week 6 (± 3 days).

^d Samples for CMV DNA analysis only will be collected every 4 weeks from Day 1.

^e Only for females of childbearing potential; negative pregnancy test must be obtained within 14 days before administration of study treatment. May be performed by the central laboratory or the investigative site laboratory.

^f Only for females of childbearing potential. Must be conducted every 4 weeks from Day 1.

^g Optional for subjects enrolled in the United States.

¹ Subjects must be willing to undergo an incisional or excisional lymph node or tissue biopsy or provide a lymph node or tissue biopsy from the most recent available archival tissue. An optional biopsy should be collected at the time of progression if possible but may be collected at other times for safety or efficacy.

Table 8: Laboratory Tests: Required Analytes

Serum Chemistries	Hematology	Serology	Pregnancy Testing (Performed Locally)

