Albumin Alkaline phosphatase ALT AST Bicarbonate Blood urea nitrogen C-reactive protein Calcium Chloride Creatinine Glucose Lactate dehydrogenase Phosphate Potassium Sodium Total bilirubin Direct bilirubin (if total bilirubin is > ULN) Indirect bilirubin (if total bilirubin is > ULN) Total protein Uric acid	Complete blood count, including: Hemoglobin Hematocrit Platelet count (absolute) Red blood cell count White blood cell count Differential count, including: Basophils Eosinophils Lymphocytes Monocytes Neutrophils Absolute values must be provided for: WBC differential laboratory results: Lymphocytes Neutrophils	HBsAg HBsAg antibody Hepatitis B core antibody HBV-DNA HCV antibody HCV-RNA CMV DNA HIV antibody (immunoassay) ^a	Only for female subjects of childbearing potential (see Table 7). Pregnancy tests (serum or urine) should be repeated if required by local regulations.

Note: Additional tests may be required, as agreed by investigator and sponsor, based on emerging safety data.

^a Optional for subjects enrolled in the United States.

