- Section 9.2.2 was updated to include details of analyses on time to onset of selected TEAEs of special interest. Summaries of longest duration of selected TEAEs of special interest were added to have a better understanding of the safety profile in terms of duration of class-effect AEs as well as AEs influenced by treatment regimens. "Grade 2 or higher" was changed to "Grade 3 or higher" for time to onset summary of rash. This change was made to be consistent with other PI3K inhibitors, which highlighted more severe cutaneous reactions graded as Grade 3 or higher in the labeling. "Herpes simplex virus infection" was changed to "herpes simplex" based on the MedDRA coding dictionary as a broader term. Exfoliative dermatitis was added to the list of TEAEs of special interest.

- Section 9.2.3 was updated to include summary of TEAEs by PT and maximum severity in decreasing order of frequency, summary of longest duration of selected TEAEs of special interest, and additional supporting summaries during the INCB050465 initial QD dosing period and the maintenance dosing period, which will provide supportive data of the safety profile of the maintenance dose. Summary of nonserious TEAEs by SOC and PT was removed because it will not be used for the clinical study report but will be provided for result disclosure.
- Section 9.3.2 was modified to include ALT and AST in the line graphs as additional supportive analyses for laboratory events of special interest.
- Section 9.3.3 was added to identify potential Hy's law events to better monitor liver toxicity.
- Section 9.3.4 was updated to align with the analysis plan for adverse events of special interest. Summary of worsening of laboratory events of special interest was removed because this is covered by the summary of worsening of laboratory abnormalities.
- Section 9.5 was updated to change the high threshold of QTcF and QTcB interval from 460 to 450 milliseconds for purpose of analysis. This change is to comply with the categories outlined in FDA Guidance for Industry (E14 Clinical Evaluation of QT/QTc Interval Prolongation and Proarrhythmic Potential for Non-Antiarrhythmic Drugs) used to characterize outliers in OTc values.

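### The Hy's law listing in SAP 9.3.3 has no time window, so it can omit a participant whose bilirubin rises only after ALT/AST has fallen to 3 × ULN or below

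*SAP*

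**What the plan says.** SAP 9.3.3 sets three conditions. It starts from "Participants with elevated ALT or AST" above 3 × ULN, requires alkaline phosphatase below 2 × ULN, and requires that these be "accompanied by total bilirubin" above 2 × ULN. All must hold "at the same visit will be listed by treatment group". The section gives no number of days. It does not say how unscheduled, repeat or local draws are assigned to a visit, but it does not restrict itself to scheduled visits either. The output is Listing 2.8.5 in SAP Appendix A.

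The purpose is stated in SAP 11.2: under Amendment 1, Section 9.3.3 "was added to identify potential Hy's law events to better monitor liver toxicity".

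The protocol decides when these values are collected:

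- Table 7 schedules chemistry every 4 weeks through Week 48 (± 3 days) and every 12 weeks after that (± 1 week).
- Table 8 places the liver tests in one required chemistry panel. The list opens "Albumin Alkaline phosphatase ALT AST Bicarbonate", and total bilirubin is further down the same list.
- Table 3, for Grade 3 ALT/AST (above 5 × ULN), says "Interrupt INCB050465 and monitor weekly until the toxicity has resolved" to Grade 1 or lower. It does not name the analytes to be repeated.
- Section 6.6 allows unscheduled visits with whatever laboratory tests are appropriate.
- Section 7.5.6 sends unscheduled draws to the central laboratory unless otherwise specified. It admits a local result to the eCRF only if there is no accompanying central result and the local one changed management or was an AE or SAE.

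**The concern.** The listing is a screen for potential events, so omitting a participant who deserves review costs more than adding one who turns out to be of no interest. A same-visit rule is at its least sensitive when aminotransferases rise first and bilirubin follows. By the time bilirubin crosses its threshold, ALT/AST may be back at 3 × ULN or below, and then neither draw satisfies all three conditions.

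The gap is not limited to Grade 3 elevations. ALT/AST above 3 but not above 5 × ULN meets the threshold in SAP 9.3.3 yet lies below Grade 3 as Table 3 gives it, so the weekly repeats are not triggered. Without an unscheduled visit, the next chemistry panel is then about 4 weeks away, or 12 weeks after Week 48.

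At stake is how an empty Listing 2.8.5 would be read. It is the only planned display that pairs aminotransferases with bilirubin.

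**Working it through.** The documents give no figure to reproduce here. The check applies the rule to constructed cases and then looks at timing.

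**Rule logic.** Under SAP 9.3.3 a participant is listed if any one draw has ALT or AST > 3, ALP < 2 and bilirubin > 2 (multiples of ULN). The alternative also lists a participant with ALT or AST > 3 and ALP < 2 at one draw and bilirubin > 2 at a draw from 0 to w days later. It was tried with w = 7, 14, 28 and 30. ALP is 1.2 × ULN throughout.

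| Case | Day 0 | Later draw | Same-visit rule | With window |
|---|---|---|---|---|
| 1 | ALT 8, bilirubin 1.2 | Day 7: ALT 4, bilirubin 2.5 | Listed | Listed |
| 2 | ALT 8, bilirubin 1.2 | Day 7: ALT 2.8, bilirubin 2.5 | Not listed | Listed, w ≥ 7 |
| 3 | ALT 4, bilirubin 1.0 | Day 28: ALT 1.5, bilirubin 2.5 | Not listed | Listed only if w ≥ 28 |
| 4 | ALT 8, bilirubin 1.2 | Day 5: ALT not drawn, bilirubin 2.5 | Not listed | Listed at all four windows |
| 5 | ALT 8, bilirubin 2.4 | none | Listed | Listed |

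Cases 1 and 2 differ only in ALT at the later draw, and that alone decides whether the participant appears.

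**Could ALT plausibly fall that fast?** The documents give no rate of decline. Assume a half-time h of 2 to 7 days. The time to reach 3 × ULN from a peak P is h × log2(P/3):

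- P = 5: log2(5/3) = 0.737, giving 1.5 to 5.2 days.
- P = 8: log2(8/3) = 1.415, giving 2.8 to 9.9 days.
- P = 15: log2(15/3) = 2.322, giving 4.6 to 16.3 days.

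At a draw one week after the peak, ALT would be below 3 × ULN throughout the assumed range when P = 5, and only for the shorter half-times when P = 8 or 15. A miss is plausible but not certain.

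**What a window can reach.** Before Week 48, consecutive scheduled visits can be 28 + 3 + 3 = 34 days apart, so a 30-day window can fall short of the next scheduled visit. After Week 48 the closest two scheduled visits can be is 84 − 7 − 7 = 70 days, so only unscheduled draws would fall inside 30 days.

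**Other displays.** Listings 2.8.2 and 2.8.4 hold the chemistry values and the abnormal ones but apply no pairing criterion. SAP 9.3.4 covers ALT, AST and neutrophils, not bilirubin. The shift tables in SAP 9.3.2 work one analyte at a time.

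**The case against.** The strongest reply is that the trial's sampling already favours same-visit detection. The liver tests share one panel and SAP 9.3.3 is not confined to scheduled visits. If the weekly repeats after Grade 3 ALT/AST use the full panel, each is a further chance to meet the rule while ALT/AST is still raised. This stands. A reader might infer that any bilirubin rise found at a later draw is missed, that the weekly repeats cause this by design, or that same-visit pairs are a matter of chance. The documents support none of these: case 1 is listed, and every complete panel yields a pair.

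Second, the data are not lost. The values appear in Listings 2.8.2 and 2.8.4. ALT and AST at or above 5 × ULN are events of special interest in Protocol 8.5, and Table 3 requires medical monitor approval to restart after Grade 3. Such participants would therefore receive individual attention. This also stands, although it does not cover elevations between 3 and 5 × ULN and provides no paired display.

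Third, few participants are likely to be affected. Protocol 1.3 reports no liver function abnormality above Grade 1 on treatment among 63 subjects in the earlier study. That favours a low severity.

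Fourth, a window brings in noise. Inclusion criterion 9d admits participants with Gilbert's syndrome and raised bilirubin, so pairing across visits may join unrelated elevations. This is a reason to flag the added participants separately, not to leave them out.

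**Conclusion.** The point holds in a narrow form. The same-visit rule omits a participant whose bilirubin exceeds 2 × ULN only when ALT/AST is at 3 × ULN or below, or was not drawn or recorded. Because no other planned display pairs the values, Listing 2.8.5 could be empty although both thresholds were crossed in sequence. That works against the purpose stated for adding the section.

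A reader might go further and say that the listing can be empty when a Hy's law case exists, or that it will lead to a false report of none. The documents do not support that. They define a potential event only by the same-visit rule, so calling a sequential pattern a case needs a definition they do not contain, and how the report would word an empty listing is unknown.

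The number affected cannot be estimated from the documents. The timing argument rests on assumed half-times of 2 to 7 days. The primary endpoint, the sample size and all efficacy estimates are untouched. This is an inexpensive improvement to a safety display, not an error in the analysis.

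**What to change.** In SAP 9.3.3, keep the present same-visit listing and add a second, separately flagged group: participants whose total bilirubin exceeds 2 × ULN within a prespecified window after an ALT or AST value above 3 × ULN. State three things with it:

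- **Window length.** The documents give none, so the sponsor must choose and justify it. Thirty days is one example; a window meant to reach the next scheduled visit before Week 48 would need to cover 34 days.
- **Alkaline phosphatase.** Judge the below 2 × ULN condition at the draw with the ALT/AST elevation.
- **Eligible draws.** Scheduled, unscheduled and recorded local values all count.

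The cost is a few sentences in the SAP, a minor programming change to Listing 2.8.5, and a few more participants to review, possibly including unrelated bilirubin elevations such as Gilbert's syndrome. Nothing in the current listing is lost. A window does not make up for sparse sampling: after Week 48 it helps only where unscheduled draws were taken.

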#### 9.3.4. Worsening Laboratory Events of Special Interest

Laboratory events of special interest are listed below.

- ALT increased
- AST increased
- Absolute neutrophil count decreased

The time to onset of a worsening laboratory event is defined as the interval between the date of first dose of study drug and the date of the first occurrence of CTC grade worse than baseline for the laboratory event. Participants who have not experienced a worsening laboratory event at the time of analysis will be right-censored at the last postbaseline study visit with nonmissing CTC grade of the laboratory event.

Time to onset of worsening Grade 3 or 4 laboratory events of special interest will be summarized using descriptive statistics and the life-table method as described in Section 9.2.2, and the Kaplan-Meier plot of time to onset of worsening Grade 3 or 4 absolute neutrophil count decreased will be provided. Laboratory events of special interest to be summarized may be adjusted based on emerging data.

# 9.4. Vital Signs

Values at each scheduled visit, change, and percentage change from baseline for vital signs, including weight, systolic blood pressure, diastolic blood pressure, pulse, body temperature, and respiratory rate will be summarized descriptively.

Normal ranges for vital sign values are defined in Table 4. The abnormal values for participants exhibiting vital sign abnormalities will be listed along with their assigned treatment regimen. Alert vital signs are defined as an absolute value outside the defined normal range and percentage change greater than 25%. Note that the definition of alert vital signs does not apply for body temperature and weight. The abnormal values for participants exhibiting alert vital sign abnormalities will be listed.

Table 4: Normal Ranges for Vital Sign Values

Parameter	High Threshold	Low Threshold
Systolic blood pressure	≤ 155 mmHg	≥ 85 mmHg
Diastolic blood pressure	≤ 100 mmHg	≥ 40 mmHg
Pulse	≤ 100 bpm	≥ 45 bpm
Temperature	≤38°C	≥ 35°C
Respiratory rate	≤ 24 breaths/min	≥ 12 breaths/min

# 9.5. Electrocardiograms

Twelve-lead ECGs including PR, QRS, QT, QTcB, QTcF, and RR intervals will be obtained for each participant during the study. Values at each scheduled visit, change, and percentage change from baseline will be summarized for each ECG parameter. Baseline will be determined as the average of all nonmissing values before the first administration of INCB050465.

Normal ranges for ECG values are defined in Table 5. Electrocardiogram values will also be considered abnormal if the absolute percentage change from baseline is more than 25% (30% for QRS interval). Participants exhibiting ECG abnormalities will be listed with study visit and assigned treatment regimen. Abnormal values for participants with alert ECG values, defined as both the absolute value and the percentage change from baseline being outside normal ranges, will be identified and listed. Outliers of QT, QTcB, and QTcF values, defined as absolute values > 450 milliseconds or change from baseline > 30 milliseconds, will be summarized.

**Table 5:** Normal Ranges for Electrocardiogram Values

Parameter	High Threshold	Low Threshold
PR	≤ 220 ms	≥ 75 ms
QRS	≤ 120 ms	≥ 50 ms
QT	≤ 500 ms	≥ 300 ms
QTcB, QTcF	≤ 450 ms	≥ 295 ms
RR	≤ 1330 ms	≥ 600 ms

QTcB = Bazett's correction; QTcF = Fridericia's correction.

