7.5.4. Electrocardiograms

All 12-lead ECGs will be performed with the subject in a recumbent or semirecumbent position after 5 minutes of rest. Baseline ECGs will be obtained during screening using a single measurement but can be performed in triplicate if the single QTc measurement is > 450 milliseconds (corrected by Fridericia; see Section 3.2). Electrocardiograms will also be obtained during the Day 1 visit (triplicate measurements) before the subject receives the first dose of study drug. Triplicate ECGs will be performed predose and 1.5 hours (± 15 minutes) after receiving study treatment at the Week 4 visit. When triplicate ECGs are being obtained, individual measurements should be performed 5 minutes (± 3 minutes) apart. All 12-lead ECGs obtained at subsequent timepoints (single measurements) will be compared with the baseline 12-lead ECGs as follows:

- For ECG morphology, all postdose ECG recordings will be compared with Day 1 predose ECGs.
- For the calculation of changes in cardiac intervals (eg, QT interval), the intervals from the screening and Day 1 predose (triplicate) ECGs will be computed and averaged and used as the baseline for comparison of all postdose intervals.

If a single measurement demonstrates a QTc interval > 500 milliseconds, 2 more ECGs should be obtained over a brief period, and the averaged QTc intervals should be used to determine whether the study treatment should be interrupted.

Twelve-lead ECGs will be acquired using an ECG analysis system with analysis and printing capabilities, as well as digital transmission capabilities to a central capture module at the ECG laboratory. The investigator and research staff will receive adequate training by a qualified person on the use and operation of the analysis system. The successful digital submission of a 12-lead ECG, meeting quality standards, to the central ECG laboratory by the site must be ensured before enrollment of the first subject. The study reference manual for procedures that must be followed for the recording and transmission of ECGs and the operator's manual with instructions for operating the digital capture module will be shipped to the site along with the device. The 12-lead ECGs will be interpreted by the investigator at the site and will be used for immediate subject management. The decision to include or exclude a subject or discontinue a subject's participation in the study based on an ECG flagged as "Abnormal, Clinically

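### The SAP's ECG alert rule can leave a QTc above 500 ms out of the alert listing, because it also requires a change of more than 25% from baseline

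*SAP*

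**What the plan says.** SAP 9.5 sets three levels of ECG reporting.

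- **Abnormal.** A value outside Table 5 (QTcB and QTcF: 295 to 450 ms) is abnormal. A percentage criterion is added: "Electrocardiogram values will also be considered abnormal if the absolute percentage change from baseline is more than 25% (30% for QRS interval"). Either one is enough. "Participants exhibiting ECG abnormalities will be listed with study visit and assigned treatment regimen"; this is Listing 2.10.2.
- **Alert.** Listing 2.10.3 covers "alert ECG values, defined as both the absolute value and the percentage change from baseline being outside normal ranges". Here both conditions must hold.
- **Outlier.** "Outliers of QT, QTcB, and QTcF values, defined as absolute values > 450 milliseconds or change from baseline > 30 milliseconds, will be summarized"; this is Table 3.5.8.

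Protocol 9.4.2.4 and its Table 11 identify notable ECGs on absolute thresholds alone (QTcF above 450 ms) and contain no percentage condition. Protocol 7.5.4 adds an on-study level: "If a single measurement demonstrates a QTc interval > 500 milliseconds, 2 more ECGs should be obtained over a brief period". The averaged value then informs whether treatment is interrupted.

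**The concern.** QTc varies over a narrow range relative to its size, so 25% of it is a very large change. Joining that condition to the 450 ms limit makes the percentage condition the binding one for every baseline above 360 ms. The alert threshold then rises with baseline: the closer a participant starts to the upper limit of normal, the higher QTc must go before it counts as an alert. Above a baseline of 400 ms the threshold exceeds the protocol's own 500 ms level.

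What is at stake is how Listing 2.10.3 is read. A listing titled as alert ECG values invites the reader to treat an empty QTc section as a sign that nothing of note occurred. It cannot bear that weight if values above 500 ms can be missing from it.

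**Working it through.** **Inputs from the documents.** The upper QTc limit is 450 ms (SAP Table 5) and the percentage limit is 25% (SAP 9.5). For baseline: "Baseline will be determined as the average of all nonmissing values before the first administration of INCB050465". Screening QTcF above 450 ms is excluded, apart from the allowance for an average of three ECGs (Protocol 3.2). The repeat-ECG level is 500 ms (Protocol 7.5.4). The plan gives no figure for how often the alert should fire, so there is none to reproduce.

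**Step 1: threshold.** A high-side alert requires value > max(450, 1.25 × baseline).

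| Baseline (ms) | Alert above (ms) | Rise needed (ms) |
|---|---|---|
| 360 | 450 | 90 |
| 380 | 475 | 95 |
| 400 | 500 | 100 |
| 420 | 525 | 105 |
| 440 | 550 | 110 |
| 450 | 562.5 | 112.5 |

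Below a baseline of 360 ms the 450 ms limit binds and the rise needed is again more than 90 ms (350 ms needs 100). So 90 ms is the minimum.

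**Step 2: comparison with 500 ms.** 1.25 × baseline exceeds 500 when baseline exceeds 500/1.25 = 400 ms. Example: 420 to 510 ms is 90/420 = 21.4%, which is under 25%, so it is not an alert. A value of 510 ms is an alert only from a baseline below 510/1.25 = 408 ms.

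Steps 1 and 2 need no assumption about the data.

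**Step 3: illustration of size.** The documents give no QTc distribution, so these inputs are assumptions: baseline QTcF normal with mean/SD 400/20, 410/20 or 420/18 ms, truncated at 450 ms; within-subject SD 12 or 20 ms; one postbaseline reading. Ranges are across the six combinations.

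| True mean shift | P(alert) per reading | P(outlier rule met) per reading |
|---|---|---|
| +30 ms | at most 0.03% | 53% to 64% |
| +60 ms | 0.02% to 2.5% | 94% to 99.6% |
| +90 ms | 13% to 31% | close to 100% |

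With no shift the alert probability is essentially zero. At +60 ms, 4% to 20% of readings exceed 500 ms, and 86% to 99.9% of those are not alerts.

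**Step 4: trial level.** With 120 participants, one reading each and independence, P(at least one alert) = 1 − (1 − p)^120.

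- At +60 ms: p = 0.00023 gives 2.7%, and p = 0.0253 gives 95%. The expected number of alerts is 0.03 to 3.0.
- At +90 ms: 120 × 0.126 = 15 to 120 × 0.311 = 37 alerts are expected.

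ECGs are repeated (Protocol Table 6: Week 4, Week 12, then every 12 weeks), so actual counts would be higher.

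**The case against.** The strongest reply is that this is one secondary descriptive listing and the same SAP section plans more sensitive outputs. That stands. The 420 to 510 ms case meets both limbs of the outlier rule (510 > 450; +90 > 30) and appears in Listing 2.10.2 with its value. By-visit summaries include the maximum (SAP 5.1), and Table 3.5.9 summarises clinically significant ECG abnormalities. An abnormal result that required a change in study drug would be an adverse event under Protocol 8.1.1.

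Three stronger readings are tempting, and the documents do not support them.

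- *The alert listing will be empty whether or not the drug prolongs QTc.* Step 4 shows otherwise: alerts are near certain at +90 ms, and at +60 ms the answer depends on the assumed spread.
- *No planned output isolates QTc above 500 ms.* This cannot be checked. Tables 3.5.8 and 3.5.9 are marked as standard and follow a set of standard tables that is not in the documents. What can be said is that the SAP text states no such category.
- *SAP 9.4 relaxes the same rule for other measures and so sets a precedent.* It says "Note that the definition of alert vital signs does not apply for body temperature and weight". Those two measures have no alert at all, rather than a looser one.

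Two further limits apply. The insensitivity is shown for QTc only: PR from 160 to above 220 ms, or RR from 850 to below 600 ms, does fire. And Protocol 7.5.4 acts on the average of three ECGs, so a single value above 500 ms is the trigger for repeats and does not by itself settle the interruption decision.

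**Conclusion.** The point holds for the alert listing and goes no further. By arithmetic alone, a participant with a baseline above 400 ms can exceed the protocol's 500 ms level without appearing in Listing 2.10.3, and no rise below 90 ms can produce a high-side QTc alert. Under the assumed distributions, the listing catches at most about 2.5% of readings at a true shift of 60 ms. It is therefore insensitive to rises up to about that size, and an empty QTc section is not evidence against prolongation.

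The conclusion rests on one inference: that the 25% limit in SAP 9.5 is the range meant for percentage change in the alert definition. SAP 9.5 does not say so outright, but it offers no other limit for QTc, and SAP 9.4 uses 25% explicitly for vital-sign alerts. The probabilities in Steps 3 and 4 rest on assumed distributions and were worked for QTcF only.

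Severity is minor. This is a safety-reporting improvement; QTc prolongation would be visible elsewhere in the report, and no efficacy endpoint is affected.

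**What to change.** In SAP 9.5:

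1. Keep the present alert rule and add that any postbaseline QTcF or QTcB above 500 ms is also listed as an alert, whatever the percentage change. Say whether this applies to individual readings or to the average of replicates.
2. Add the number of participants with postbaseline QTcF above 500 ms to Table 3.5.8.
3. State that the 25% limit (30% for QRS) is the one used in the alert definition.

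A larger change-from-baseline category, such as above 60 ms, is optional; nothing in the documents sets that figure. PR, QRS, QT and RR can stay as they are. These are reporting thresholds and leave the protocol's clinical rules untouched.

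The cost is a few sentences, one listing filter and one table row. The downside is that a few more values will be listed as alerts.
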